Spinocerebellar ataxia type 3 (SCA3) is the most common autosomal dominantly inherited ataxia worldwide, also called Machado-Joseph disease (MJD), caused by an over-repetition of the trinucleotide CAG within the ATXN3 gene, which confers toxic properties to ataxin-3 (ATXN3) species¹. It is a devastating neurodegenerative disorder that principally affects the deep cerebellar and pontine nuclei, basal ganglia, and spinal cord, and leading to severe disability and premature death. Clinical symptoms in SCA3 are not restricted to the deterioration in the motor domain, but non-motor symptoms (NMS), such as sleep disturbance, fatigue, neuropathy, cognitive decline, depression, and bladder disturbance.². Currently, no specific pharmacological and treatments can alter natural course of the disease. Cerebellar transcranial alternating current stimulation (tACS) is an increasingly easy-used, safe, cheap, and noninvasive tool in neuroscience that is able to modulate cerebellar excitability³⁻⁵. Computational modeling studies have demonstrated the biophysical feasibility of modulating cerebellar structures using tACS with only negligible spreading effects to neighboring regions⁶. Initially, this technique has been successfully applied in healthy volunteers to investigate the neural correlates of motor learning and cognitive and emotional processes⁷⁻¹⁷. More recently, studies also started to explore its therapeutic potential in a variety of neurological conditions, such as Parkinson's disease ^{18,19}, Alzheimer's disease^{20,21}, epilepsy²², schizophrenia²³, depression²⁴, insomnia²⁵, and stroke²⁶. No serious adverse events of cerebellar tACS have been reported in these and other studies and it is therefore considered a safe and tolerable method ²⁷. Possible side effects mainly include a transient optical illusion, itching, tingling, or mild burning sensation underneath the electrodes²⁷. Inspired by these promising findings, we designed the clinically-oriented SCA3-tACS, randomized, parallel sham-controlled clinical trial to explore whether cerebellar tACS decreases ataxia severity and a variety of non-motor symptoms in a homogeneous cohort of SCA3 patients and if so,

what the duration of this beneficial effect is.

Methods

Ethics and dissemination

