This is a single-centre, triple-blind, randomised, sham-controlled intervention trial. A total of at least 80 recruited participants with SCA3 will be randomly and equally assigned to the active or sham treatment group. The randomization was created by a computer program in permuted blocks of four and managed by an offsite statistician who does not participate in this study. Every participant gets an unknown-beforehand number from a sealed opaque envelope, which determines the trial he/she will participate in. The envelopes for the two tACS plans (sham and active) have the same characteristics regarding size, color, appearance, weight, and odor, and different plans are numbered by the statistician. All participants were blinded to the specific assignment during the triple-blind treatment period until the end of the follow-up, except for any emergency when the blinding will be stopped. Participants will receive a 2-week intervention, followed by a 4-week follow-up (conducted at the 6th week, T2) and a 12-week follow-up (conducted at the 14th week, T3). The entire process will strictly follow the consolidated standards of reporting trials guidelines (Figure 1) and standard protocol items: recommendations for interventional trials checklist^{28,29}.

[figure not shown]

FIGURE 1 Design and flow of participants through the study.

Termination of the trial will be decided by the principal investigators, according to the following criteria: (1) lack of two consecutive tACS sessions, (2) severe adverse events (AEs), and (3) affected tACS-Assessment by treatment of other diseases. If a patient is lost to follow-up at T2 or T3, the data collected up to that point will still be used in the statistical analysis at T2/T3.

Sample size calculation

Positive effect is supposed to occur in both groups according to previous report³⁰. The primary clinical remission criterion defined a ≥ 1.5 points SARA score decrease caused by 2 weeks of treatment. The SARA scores were expected to increase in 25% of placebo patients and 60% of the treated patients. 80% power was tested for 36 patients in each group, with a 35% δ between the groups, by using a 2-sided test and at the 5% level. Taking 10% attrition rate in consideration, 40 patients for each group will be needed to reach a minimum total sample size of 72. Based on these calculations, we estimate that at least 80 SCA3 participants will enroll in the study.

Transcranial alternating current stimulation intervention

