Participants were assessed at the end of each treatment session for adverse events (AEs), vital signs, and discomfort ratings (for potential scalp sensations associated with CB-tACS) using the commonly used questionnaire in CB-tACS trials, with telephone call every 2 weeks to record AEs during follow-up. Participants were instructed to report any additional adverse

events experienced during or after treatment that were not included in the questionnaire.

Outcomes

Primary outcome measurement

Efficacy outcome. The primary outcome measurement was the proportion of participates with clinical remission at the completion of treatment (defined as the reduction of SARA score at least 1.5 point from baseline).

The secondary outcome measures were proportion of patients with clinical remission at T2 and T3, and the changes at different timepoints (T1, T2, T3) from T0, compared to sham stimulation, including SARA, ICARS, EQ-5D, and gait variability. The safety outcomes included vital signs (blood pressure, body temperature, heart rate, pulse), adverse effects linked to tACS.

Data management And Quality Control

To ensure the rigor of this study, the whole process will be carried out strictly according to Guidelines for Good Clinical Practice of the International Conference on Harmonisation (ICH). Data will be collected from T0, T1, T2, and T3, respectively. All investigators, trial supervisors, and raters involved in the study must be trained before they participate in communicating and instructing participants, assessing, collecting data, and completing the CRF. Double entries of data into the software Yidu Research platform (Yiducloud (Beijing) Technology Ltd.) will be finished by two independent investigators, and these electronic data will be stored on a secure university server with regularly back-up and password protection. Yidu Research platform has an authority management mechanism associated with personnel and roles and a strict data audit mechanism to fully protect the security of data utilisation. Double-check will be performed to correct inconsistent entries or typos. The details of the quit participants, including reasons, date, AEs, and duration of the treatment, will be recorded. The final trial dataset, including the intent-to-treat and per-protocol dataset will be analyzed by an independent statistician.

Data analysis

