Baseline characteristics will be summarized and presented using appropriate descriptive statistics. Normality of the variables will be assessed by using the skewness statistic and normal probability plot. Baseline characteristics between two groups will be compared using independent–t test for continuous variables and the χ^2 analysis or Fisher's Exact test for categorical variables. Generalized estimating equations (GEE) ⁴⁰ analysis will be adopted to adjust for any significant differences in baseline characteristics. Baseline characteristics of the participants who completed the study will be compared with those who did not finish the study. All primary and secondary outcomes will be compared between groups on the basis of intention–to–treat (ITT) principle. GEE models will be used to assess differential change of each primary and secondary outcomes across different time–points between two groups and within group from baseline. IBM SPSS 26.0 software will be used for all statistical analysis. Two–tailed test will be used and statistical significance will be set at a p–value < 0.05. Intention-to-treat (ITT) refers to all eligible patients who were randomized to treatment, include drop-out cases.

Per-protocol (PP) refers to the set of cases that have completed the overall study protocol, a subset of the FAS in which each subject in the dataset is a valid case or sample with good adherence, no protocol violations, and complete baseline values for key indicators.

Missing data

Due to the long duration of intervention and the long follow-up period, so there may be a lot of missing data. If missing data were found, the percentage of missing data will be reported, the potential patterns of missing data should be examined, and appropriate method should be used for multiple imputation of missing data. The multiple imputation method will be preferred for analyzing the missing data, and the complete-case data should be reported in the manuscript as sensitivity analysis.

Analysis of primary outcome

The Type I error rate (α -level) used in the assessment of χ^2 analysis or Fisher's Exact test for the primary efficacy outcome is 5%. The assessment of significance for the A-tACS versus StACS contrasts will use χ^2 analysis or Fisher's Exact test, based on ITT, PP, and sensitivity analysis (multiple assumptions for the missing value).

Analysis of secondary outcomes

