Per-protocol (PP) refers to the set of cases that have completed the overall study protocol, a subset of the FAS in which each subject in the dataset is a valid case or sample with good adherence, no protocol violations, and complete baseline values for key indicators. Missing data

Due to the long duration of intervention and the long follow-up period, so there may be a lot of missing data. If missing data were found, the percentage of missing data will be reported, the potential patterns of missing data should be examined, and appropriate method should be used for multiple imputation of missing data. The multiple imputation method will be preferred for analyzing the missing data, and the complete-case data should be reported in the manuscript as sensitivity analysis.

Analysis of primary outcome

The Type I error rate (α -level) used in the assessment of χ^2 analysis or Fisher's Exact test for the primary efficacy outcome is 5%. The assessment of significance for the A-tACS versus StACS contrasts will use χ^2 analysis or Fisher's Exact test, based on ITT, PP, and sensitivity analysis (multiple assumptions for the missing value).

Analysis of secondary outcomes

The Type I error rate (α-level) used in the assessment of pair-wise treatment comparisons for the primary efficacy outcome is 5%. All secondary outcomes will be compared between groups on the basis of intention–to–treat (ITT) principle. GEE models will be used to assess differential change of each secondary outcomes across different time–points between two groups and within group from baseline.

ALFF, ReHo, and FC Analysis

Statistical analysis of MRI data was performed using Matlab2013b, SPM12

(https://www.filion.ucl.ac.uk/spm/) (Sidhu et al. 2016). The Flexible factorial of second-order analysis was used to design the statistical matrix and to set the three factors of subjects, groups, and time. Groups and time were fixed factors, and the serial number of subjects was a random factor. Then, the interaction matrix of groups × time to analysis was set to determine the intergroup interaction effect. The resulting statistical map was set at p<0.05 (AlphaSim correction) with a combined voxel p<0.001. Use RestPlus toolbox

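### Does the sentence on patients lost at T2 or T3 carry earlier values forward, against the planned multiple imputation?

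*Protocol*

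**What the plan says.** The SCA3 and MSA protocols share the same text on this point.

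- **Trial design, paragraph on termination (just before Sample size calculation).** When a patient drops out at either follow-up visit, "the data collected up to that point will still be used in the statistical analysis at T2/T3". No method is attached to the sentence.
- **Missing data.** Both protocols name the method here: "The multiple imputation method will be preferred for analyzing the missing data, and the complete-case data should be reported in the manuscript as sensitivity analysis".
- **Data analysis.** The analysis population keeps drop-outs: "Intention-to-treat (ITT) refers to all eligible patients who were randomized to treatment, include drop-out cases". GEE models compare the arms across the visits.
- **Outcomes.** The primary outcome is at the end of the two-week treatment (T1) in both protocols. In SCA3, "The secondary outcome measures were proportion of patients with clinical remission at T2 and T3". Changes in the rating scales, quality of life and gait at T1, T2 and T3 are also secondary, in both.
- **Introduction.** Each trial also asks, if there is a benefit, "what the duration of this beneficial effect is".

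**The concern.** The doubt comes from the last words of the sentence. Had it said only that earlier data are kept, nothing could be misread. It places data gathered before the loss in the analysis at T2/T3, where the patient has no value, and does not say how. One analyst could read this as permission to put the T1 value in the empty T2 or T3 cell. Another would go to the Missing data section and impute. The two could report different T2 and T3 results, each citing the protocol.

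Carrying T1 forward would also presuppose what the follow-up is meant to find out. It treats a patient's response at the end of treatment as still present one or three months later, and the trial asks how long the benefit lasts. If the active arm lost more of its T1 response than sham did, carry-forward would flatter the active arm on the outcomes that answer this question.

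**Working it through.** **Step 1: the texts side by side.**

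| Place | What it settles | Fits keeping the data? | Requires carry-forward? |
|---|---|---|---|
| Paragraph on termination | Data from patients lost later are still used | Yes | No |
| Data analysis, ITT definition | Drop-outs stay in the set | Yes | No |
| Data analysis and Analysis of secondary outcomes, GEE | Observed visits contribute to a longitudinal model | Yes | No |
| Missing data | Multiple imputation preferred, complete cases as sensitivity | Yes | No |

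A multiple imputation of T3 would normally draw on the patient's T0, T1 and T2 values. Earlier data are then used in the analysis at T3 in the plain sense of the words. A patient lost at T3 also has a T2 value, which is analysed at T2. The sentence is satisfied without any substitution.

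**Step 2: the size if carry-forward were applied (SCA3).**

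Inputs from Sample size calculation: T1 remission 60% active and 25% sham, 40 per arm, attrition 10%. All T3 rates below are assumptions, because the protocol gives none.

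The protocol's own sample size reproduces. For 25% against 60%, two-sided 5% and 80% power, the formula with continuity correction gives 36 per arm (exact Fisher power 79.7%), and 36/0.9 = 40. The present question does not depend on it.

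With a fraction *d* lost after T1, the rate seen at T3 in an arm under carry-forward is (1 − d) × p(T3) + d × p(T1).

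- **Complete fade (25% in both arms), d = 0.10.** Active: 0.9 × 25% + 0.1 × 60% = 28.5%. Sham: 25%. False difference: 3.5 points.
- **Complete fade, half the losses before T1 and counted as non-responders.** Active: 0.9 × 25% + 0.05 × 60% = 25.5%. Sham: 0.9 × 25% + 0.05 × 25% = 23.75%. False difference: 1.75 points.
- **Half fade (42.5% against 25%), d = 0.10.** Active: 0.9 × 42.5% + 0.1 × 60% = 44.25%. The difference is 19.25 points against a true 17.5.
- **Persistence (60% against 25%).** The rates are unchanged. Bias 0.
- **Equal fade (45% against 10%), d = 0.10.** Active: 0.9 × 45% + 0.1 × 60% = 46.5%. Sham: 0.9 × 10% + 0.1 × 25% = 11.5%. The difference is 35 points, as in truth. Bias 0.
- **40% against 10%, with dropout 5% active and 15% sham.** Active: 0.95 × 40% + 0.05 × 60% = 41.0%. Sham: 0.85 × 10% + 0.15 × 25% = 12.25%. The difference is 28.75 points against a true 30, a bias of −1.25, against active.

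Rejection rates by exact enumeration of all binomial pairs, 40 per arm, two-sided 5%, when there is no true difference at T3:

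| Case | Chi-square | Logit Wald (the form of a GEE visit contrast) | Fisher |
|---|---|---|---|
| No dropout, 25% v 25% | 5.00% | 4.68% | 2.9% |
| Complete fade, all losses after T1, 28.5% v 25% | 6.35% | 6.14% | 3.9% |
| Complete fade, half the losses before T1, 25.5% v 23.75% | 5.38% | 5.0% | 3.1% |

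No size can be given for MSA, because that protocol states no T2 or T3 values and no standard deviations.

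**The case for a change.** The strongest case for a change is that the sentence appears in both protocols, neither it nor the Missing data section refers to the other, and multiple imputation is only preferred, which leaves room for another method. The SCA3 abstract also lists T2 and T3 within the primary outcome, and the primary test is chi-square or Fisher. A test at a single visit cannot use a T1 value at T3 except through imputation or substitution. Both protocols expect that much data may be missing, and under complete fade the false difference is 35 points times the fraction lost, so an assumed 20% would give 7 points. The remedy would cost one sentence in each protocol.

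The looseness of the wording stands, and so does the arithmetic. The conflict does not. It arises only if a method is read into a sentence that states none, and the section written for missing data does name one. The argument from the single-visit test leads to the same place, because multiple imputation is the route the protocol gives for filling the T3 cell. The abstract's listing of visits is a separate inconsistency; the Outcomes section puts SCA3 remission at T2 and T3 among the secondary outcomes. A replacement sentence would restate the method already planned and would alter no analysis.

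**Conclusion.** The concern does not call for a change. An analyst who follows the protocol keeps the earlier data of lost patients, takes the method for missing T2 and T3 values from the Missing data section, and reports complete cases as sensitivity. That is a sound analysis of the follow-up visits.

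The largest distortion found at the protocol's 10% attrition is 3.5 points, with a chi-square false-positive rate of 6.35%. It needs several conditions at once: values carried forward, the active effect gone entirely by T3, sham unchanged, and every loss after T1. Moving half the losses before T1 halves the distortion to 1.75 points, and other plausible patterns give zero or the opposite sign. It would touch secondary outcomes only, as the Outcomes sections define them.

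The conclusion rests on reading the sentence as a statement that data are retained, which its place at the end of a paragraph on termination and losses supports. The sponsor may tidy the wording when the text is next revised, but no error and no change of result is established.

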and then continue walking until I tell you to stop. Walk at your normal speed, as if you were walking down the street to go to the store." Gait parameters were measured using two ninedimensional (three-axis accelerometers + three-axis gyroscopes + three-axis magnetometers) Inertial Measurement Unit (BWT901CL, WIT-MOTION, Shenzhen, China), as well as two flexible pressure sensor insoles. Use Visual Studio software (Visual Studio 2017, Microsoft, the USA) was used to synchronize timestamp and task data and to process the raw data. Participants completed the walk three times at their selected speed and the mean and standard deviation of gait parameters, including stride time variability, double support time variability, toe-out angle variability, and toe-off angle variability were determined. A detailed description of the technical devices is provided elsewhere. ³⁹

Adverse Events

Participants were assessed at the end of each treatment session for adverse events (AEs), vital signs, and discomfort ratings (for potential scalp sensations associated with CB-tACS) using the commonly used questionnaire in CB-tACS trials, with telephone call every 2 weeks to record AEs during follow-up. Participants were instructed to report any additional adverse events experienced during or after treatment that were not included in the questionnaire.

Outcomes

Primary outcome measurement

The primary outcome was the change from baseline to week 2 in the Unified Multiple System Atrophy Rating Scale (UMSARS) total score (sum of parts I and II). PMID: 15452868. Higher UMSARS scores denote poorer health.

The secondary outcomes included the change in UMSARS part II (UMSARS II; motor examination scores, on which scores range from 0 to 56), the changes at different timepoints (T1, T2, T3) from T0, compared to sham stimulation, including SARA, ICARS, MSA-QoL, and gait variability. The safety outcomes included vital signs (blood pressure, body temperature, heart rate, pulse), adverse effects linked to tACS.

Data management And Quality Control

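### Baseline significance tests decide which covariates enter the GEE models, so the adjustment set is not fixed and a scale's own baseline score is usually left out

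*Protocol*

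**What the plan says.** The Data analysis sections of the SCA3 and MSA protocols carry the same rule. First, "Baseline characteristics between two groups will be compared using independent–t test for continuous variables", with chi-square or Fisher's exact test for categorical ones. Then GEE "analysis will be adopted to adjust for any significant differences in baseline characteristics". The same paragraph sets the threshold: a two-tailed "test will be used and statistical significance will be set at a p–value < 0.05".

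The models that this rule feeds are described only in outline:

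- SCA3, Data analysis: "GEE models will be used to assess differential change of each primary and secondary outcomes across different time–points between two groups", so the primary outcome is included.
- Both protocols, Analysis of secondary outcomes: "GEE models will be used to assess differential change of each secondary outcomes across different" time points, between groups and within group from baseline.
- MSA, Primary outcome measurement: "The primary outcome was the change from baseline to week 2 in the Unified Multiple System Atrophy Rating Scale (UMSARS) total score", which is a continuous endpoint.

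None of these names a covariate. The designated primary test is separate: under Analysis of primary outcome, the treatment "contrasts will use χ^2 analysis or Fisher's Exact test, based on ITT, PP, and sensitivity analysis".

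**The concern.** Allocation is randomised 1:1 in permuted blocks, so a significant baseline difference is a chance finding by construction. It says nothing about whether the variable predicts outcome. Selecting covariates this way has three consequences:

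- The adjustment set is chosen by the data, and the published adjusted model depends on which chance imbalances cross 0.05.
- The one covariate almost certain to be prognostic, the T0 value of the scale being analysed, is left out unless it happens to differ significantly.
- An imbalance just short of significance is left uncorrected.

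This is not a detail left to an SAP. The protocol itself states a data-driven rule, and an SAP with fixed covariates would have to depart from it.

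The rule reaches the GEE analyses of primary and secondary outcomes in SCA3, the secondary GEE analyses in MSA, and any continuous analysis of UMSARS change. Those outcomes are already changes from T0. What is at stake is therefore the further gain from adjusting a change score for baseline, not the whole benefit of having a baseline measurement.

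**Working it through.** **Inputs from the documents.** Two-sided alpha is 0.05. SCA3 has 36 evaluable per arm (Sample size calculation). MSA has 84 in total less 10% attrition: 84 × 0.9 = 75.6, about 38 per arm.

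**Assumed.** The correlation ρ between T0 and T1 on the same scale is not given; 0.6 to 0.95 is used. T0 and T1 are taken as bivariate normal with equal variances (SD 1).

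**The plan's own figure.** The protocol gives no figure for the adjustment rule. Its SCA3 sample size does reproduce: 25% against 60%, 80% power, with continuity correction, gives 36 per arm, and 36/0.9 = 40. That calculation concerns the unadjusted primary test, which the rule does not affect.

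**Step 1: how often the trigger fires.** For one baseline score, P = 0.05 under randomisation (simulated 4.8% to 5.1%). The SCA3 protocol names eight T0 measures: SARA, ICARS, EQ-5D index, EQ-VAS and four gait variability parameters. The chance that at least one fires is 1 − 0.95⁸ = 34% if they are independent. It is 25% or 19% by simulation if their pairwise correlation is 0.5 or 0.7 (assumed).

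**Step 2: efficiency.** The variance of the change-score contrast is proportional to 2(1 − ρ), and that of the baseline-adjusted contrast to 1 − ρ². Their ratio is 2/(1 + ρ).

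**Step 3: power.** There were 40,000 simulated trials per setting. The rule was coded as ANCOVA if the baseline t-test has p < 0.05, otherwise a t-test on change. The effect was set so that the plain change score has 80% power.

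| ρ | Variance ratio | 38/arm: rule | 38/arm: fixed adjustment | 36/arm: rule | 36/arm: fixed adjustment |
|---|---|---|---|---|---|
| 0.6 | 1.25 | 81% | 88% | 81% | 87% |
| 0.7 | 1.18 | 81% | 86% | 80% | 85% |
| 0.8 | 1.11 | 80% | 83% | 80% | 83% |
| 0.9 | 1.05 | 80% | 82% | 80% | 81% |
| 0.95 | 1.03 | 80% | 80% | 80% | 81% |

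Under the null, the rule rejects in 4.3% to 4.9% of trials.

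**Step 4: uncorrected imbalance.** A baseline difference just under the trigger is t(0.975, 2n − 2) × √(2/n). It shifts the change-score estimate by (1 − ρ) times that amount. At n = 38 and ρ = 0.8 the shift is 0.2 × 1.993 × 0.229 = 0.091. The 80%-power effect is (1.993 + 0.847) × √0.4 × 0.229 = 0.412, so the ratio is 22%. Across ρ = 0.6, 0.7, 0.8, 0.9 and 0.95 the ratio is 31%, 27%, 22%, 16% and 11%.

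**The case against.** The strongest reply has five parts.

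- **Silence.** The protocol does not say that the trigger is the only source of covariates; a list could sit in the SAP. This does not rescue the rule. It is stated, no other covariate is named, and a list added elsewhere would still leave significance-triggered covariates on top of it.
- **Reach.** No designated primary test is touched. That stands and limits the weight of the point. The mismatch between a chi-square test and the continuous UMSARS endpoint is a separate problem.
- **Size.** The loss is 0 to 3 power points for ρ of 0.8 or more, and the 7-point loss needs ρ = 0.6, which the documents neither support nor exclude. The 80% starting point is a yardstick, since neither sample size calculation powers a two-week change-score test. The shift in step 4 is a worst case: at a median non-triggering imbalance (|t| about 0.64) the same formula gives 10%, 9%, 7%, 5% and 4%. All of this stands. A version of the rule with eight candidate covariates also kept its size and had essentially the power of the plain change score.
- **Model.** The simulation uses one time point, not GEE over T1 to T3. This is fair; the figures show relative efficiency and do not predict the planned model's power.
- **Timing and contrasts.** SCA3 enrolment ran to March 2023 and the document is dated June 6, 2023, so T1 data probably exist. Any change is credible only if fixed before unblinding. Removing T0 as an outcome time point need not lose the within-group contrasts: mean change per arm can be estimated from the baseline-adjusted change model.

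**Conclusion.** The concern holds. Both protocols fix a covariate rule that depends on chance imbalance, so the adjusted GEE models cannot be stated in advance. That defect does not depend on any assumption about correlation.

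The efficiency cost is modest: about 7 power points at ρ = 0.6, 3 at 0.8 and almost none at 0.95, assuming normal data, equal variances and analysis as change from T0. There is no inflation of type I error and no effect on the designated primary test or the sample size. The point should be corrected, but it does not by itself threaten the trial's primary conclusion.

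**What to change.** In the Data analysis section of both protocols, delete adjustment triggered by significant baseline differences, and present baseline characteristics descriptively without p-values.

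Pre-specify the T0 value of each scale as a covariate in its own T1–T3 model, with T0 not also an outcome time point:

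- **MSA:** UMSARS total and part II, SARA, ICARS, MSA-QoL and gait variability.
- **SCA3:** SARA, ICARS, EQ-5D and gait variability.

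For the SCA3 remission GEE, state one fixed choice: unadjusted, or adjusted for baseline SARA. A logistic model for remission at T1 adjusted for baseline SARA is an optional supportive analysis. State that within-group changes come from the same baseline-adjusted models, and date the decision before unblinding.

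The cost is wording and one model term, one degree of freedom, per scale, using T0 data already collected. If ρ is near 0.95 there is almost no gain in power, and the benefit is only that the model is fixed.

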The Type I error rate (α -level) used in the assessment of pair-wise treatment comparisons for the primary efficacy outcome is 5%. All secondary outcomes will be compared between groups on the basis of intention–to–treat (ITT) principle. GEE models will be used to assess

differential change of each secondary outcomes across different time-points between two groups and within group from baseline.

ALFF, ReHo, and FC Analysis

Statistical analysis of MRI data was performed using Matlab2013b, SPM12 (https://www.filion.ucl.ac.uk/spm/) (Sidhu et al. 2016). The Flexible factorial of second-order analysis was used to design the statistical matrix and to set the three factors of subjects, groups, and time. Groups and time were fixed factors, and the serial number of subjects was a random factor. Then, the interaction matrix of groups \times time to analysis was set to determine the intergroup interaction effect. The resulting statistical map was set at p<0.05 (AlphaSim correction) with a combined voxel p<0.001. Use RestPlus toolbox

(https://github.com/topics/restplus, version 1.2) was used to extract the values of the above abnormal brain regions, and Bonferroni tests were performed for all results with significant differences to verify between-group differences. Statistical significance was set at p<0.05. Image presentation used the xjview toolbox in Matlab 2013b.

Analysis of intra-network functional connectivity

A one-sample Student's t-test was applied to the spatial maps of all participants for each IC using the SPM12 toolbox, and regions surviving multiple comparison corrections with voxel-level family-wise error (FWE) correction (p<0.05) were saved as the specific group-level mask for each group. These four masks for each IC were then integrated into a union mask, which was used for the group comparison. A single model using a flexible-factorial design (2×2) was performed to obtain the ICs showing significant between-group differences. Regions showing significant differences (voxel-level FWE correction, p<0.05) were saved as the mask for subsequent post-hoc analyses, and the significance level was set at p<0.0125 (0.05/4) for Bonferroni correction across 4 tests.

Software and significant level of the statistical analyses

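### MRI regions selected because group×time was significant are re-tested in the same participants to verify group differences, which the re-test cannot do

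*Protocol*

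**What the plan says.** The section on ALFF, ReHo and FC analysis in the SCA3 protocol describes two steps.

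- **Selection.** A voxel-wise flexible factorial model is fitted, and the matrix of groups × "time to analysis was set to determine the intergroup interaction effect". The threshold follows: "The resulting statistical map was set at p<0.05 (AlphaSim correction) with a combined voxel p<0.001".
- **Second test.** The RestPlus toolbox "was used to extract the values of the above abnormal brain regions". Then "Bonferroni tests were performed for all results with significant differences to verify between-group differences", with the level given as "Statistical significance was set at p<0.05". Neither the contrast nor the number of tests in the Bonferroni family is stated.

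The next section, on intra-network functional connectivity, has a similar structure: "A single model using a flexible-factorial design (2×2) was performed to obtain the ICs showing significant between-group differences". Regions that survive voxel-level FWE correction "were saved as the mask for subsequent post-hoc analyses, and the significance level was set at p<0.0125 (0.05/4) for Bonferroni correction across 4 tests".

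The MSA protocol repeats both sections. For the ALFF/ReHo/FC step, neither protocol names an atlas region, a held-out sample or any other source of regions independent of these scans.

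**The concern.** A region enters the second step only because noise and effect together pushed its group×time statistic over a strict threshold. Values from that region, in the same participants and scans, carry the same noise. A further test on them mostly reports that the region was selected. Bonferroni over the selected regions allows for how many are re-tested, not for the search across the brain that found them.

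The protocol gives the second test the job of verifying the finding. A reader of the report would then take a small regional p-value, and any effect size quoted with it, as separate support for a mechanism of action. Neither can be read at face value.

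**Working it through.** **Inputs from the protocol.** Selecting contrast group×time; voxel p<0.001 with AlphaSim p<0.05; re-test at 0.05 (ALFF/ReHo/FC) or 0.05/4 = 0.0125 (intra-network, as stated). The MRI sections give no number scanned. The SCA3 sample size section gives 36 per arm before attrition. For 25% against 60%, two-sided 5% and 80% power, that figure reproduces with a continuity correction (31 without it).

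**Assumptions not in the protocol.** Two scans per participant; 36 scanned per arm with pre-post correlation r = 0.3, 0.5 or 0.7, or 18 per arm with r = 0.5; equal variance at both scans; smooth 20×20×20 volumes with a smoothing width of 3 voxels.

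**Step 1: effect size needed for selection.** With two scans, group×time is a two-sample t-test on change. A voxel is selected at two-sided p<0.001 only if |d| ≥ t(0.9995; 2n−2) × √(2/n).

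- n = 36: |d| ≥ 0.81
- n = 18: |d| ≥ 1.20

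Every selected voxel therefore shows a large apparent effect, whatever the truth.

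**Step 2: null simulation.** For each scenario, 200 maps with no true effect were generated. Clusters were formed at voxel p<0.001 with no extent threshold, giving 496 to 614 clusters per scenario, and cluster means were re-tested in the same data.

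| Scanned per arm, r | Interaction re-tested: pass at 0.05 | Mean apparent d (change) | Post-treatment groups only: pass at 0.05 |
|---|---|---|---|
| 36, 0.3 | 100% | 0.92 | 55% |
| 36, 0.5 | 100% | 0.91 | 41% |
| 36, 0.7 | 100% | 0.91 | 25% |
| 18, 0.5 | 100% | 1.37 | 37% |

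With the interaction re-tested, all clusters also passed at 0.0125 and 0.005; the largest re-test p was 0.0010. A region fixed in advance would pass 5% of the time, with expected effect 0. That benchmark follows from the level of the test and was not simulated.

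**Step 3: why the post-treatment comparison is affected too.** Under the null, the correlation between change and the post-treatment value is (1−r)/√(2(1−r)) = √((1−r)/2). This is √0.35 = 0.59 at r = 0.3, √0.25 = 0.50 at r = 0.5 and √0.15 = 0.39 at r = 0.7. Selecting on change therefore partly selects on the post-treatment difference, and less so as r rises, as in the table.

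**Step 4: clusters large enough for 5% cluster-level control.** Only 10 or 11 clusters per scenario qualified. All passed the repeated interaction test, with mean apparent d of about 1.2 (36 per arm) and 1.8 (18 per arm). On the post-treatment comparison 36% to 100% passed, which is imprecise. An extent threshold does not remove the inflation.

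**Step 5: what selection itself controls.** If AlphaSim works as intended, about 5% of null maps yield any cluster. Over three measures, if independent, the figure is 1 − 0.95³ = 14%. The re-test acts only on clusters that have already appeared and does not change these rates.

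**The case against.** The best defence is that this is ordinary post-hoc decomposition of an interaction: the corrected map carries the inference, and the regional tests show which arm or scan drives it. That use is acceptable. It is not the stated purpose, which is verification.

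Four stronger readings are tempting, and the documents do not support them.

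- *The re-test confirms almost any chance cluster.* This holds only if the selecting contrast is repeated. The protocol does not say which contrast is used, and a comparison at the post-treatment scan alone passes far fewer clusters.
- *The procedure raises the false-positive rate of the MRI analysis.* It does not. The map-level rate is set by the corrected threshold, and the simulated pass rates are conditional on a chance cluster having appeared.
- *The intra-network section selects on a group main effect, which would average in the pre-treatment scan.* The wording is ambiguous, not shown to be wrong. Four masks per component, a 2×2 layout and four tests suggest that group there means an arm-by-time cell, so the phrase may include the interaction. That section also calls its tests post-hoc and makes no claim to verify.
- *The trial's conclusions are at risk.* MRI is not among the primary, secondary or safety outcomes listed under Outcomes in either protocol.

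It also stands that the apparent effect sizes depend on an unstated number scanned, and that the protocol does not say effect sizes from these regions will be reported.

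**Conclusion.** The concern holds, as a minor point. The ALFF/ReHo/FC section in both protocols states a circular second step: it cannot verify the regions that the same data selected, and Bonferroni over those regions does not repair it. For a chance cluster, the pass rate at 0.05 is essentially 100% if the interaction is repeated and about 25% to 55% if groups are compared only after treatment, against 5% for an independent region. Apparent standardized differences are about 0.9 with 36 per arm and 1.4 with 18 per arm when the truth is zero. These figures rest on the assumed scans, numbers, correlations and smoothing, and on clusters without an extent threshold. The direction of the bias follows from the design of the step and does not depend on them. No main efficacy or safety conclusion is affected.

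**What to change.** In the ALFF/ReHo/FC section of both protocols, state that inference rests on the corrected group×time map. Replace the aim of verifying with post-hoc description of the direction of the interaction, and name the contrasts used. Label extracted values, their p-values and any effect sizes as descriptive. If confirmatory regional tests are wanted, run them in regions fixed in advance and independently of these data.

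In the intra-network section, give the post-hoc tests the same descriptive label and state that group×time is the selecting contrast.

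The change is to wording only and needs no new data. The cost is fewer regional p-values that can be reported as confirmatory.
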